7.1.3 Analysis Period

The main analysis period would be the Treatment Emergent period.

For all treatment emergent adverse events, it is defined as the period from the date of the first dose until the earliest of the following 1) date of Study Day 58; or 2) date of early discontinuation from study, or 3) data cutoff date. However, SAEs will include all the serious adverse events collected after the first dose.

The analysis period used for abnormalities in laboratory evaluations is defined as the period from the date of the first dose until the earliest of the following 1) date of Study Day 90; or 2) date of Early discontinuation from study, or 3) data cutoff date.

Analysis period for efficacy parameters would be the period from the date of the first dose until the earliest of the following 1) Date of Study Day 90; or 2) Date of Early discontinuation from study, or 3) data cutoff date.

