7.1 General Considerations

All safety analyses will be based on Safety Population; all efficacy analyses will be based on Modified Intent-to-Treat population, unless otherwise specified. Some specific sensitivity analyses of efficacy may be based on ITT and Per Protocol populations (for primary endpoints only). See Section 7.4 below for definitions of each analysis population.

All analyses will be considered as descriptive analyses. Derivation of two-sided 95% confidence intervals and p-values will be generated where applicable.

Time to event endpoints will be defined as the start date/time to the end date/time; censoring dates will be the last date/time the patient was determined to be event-free. Kaplan Meier methods will be used for time to event endpoint analyses; a log-rank test will be performed to compare the two survival curves. Timepoints estimates and median survival will be derived from the Kaplan Meier analysis. A Cox proportional hazards model may also be used to compare the two treatment arms using a hazard ratio.

Categorical endpoints will be calculated as the percentage of patients with the event, relative to the number of patients in a given analysis population (see Section 7.4). Stratified logistic regression approaches and/or repeated measures statistical approaches may be used to compare patients on the sargramostim and control arms, in addition to Fisher's Exact or Chi² tests (as appropriate). The randomization stratification factor for the baseline SOFA score (<6 versus \geq 6) will be considered for any stratified analysis.

Continuous endpoints will be summarized by n, means, medians, minimum, maximum, and 25th and 75th percentiles. Analysis of variance, analysis of covariance, and/or repeated measures statistical approaches may be used to compare patients on the sargramostim and control arms.

In the event that the underlying assumptions and/or distributions for a given statistical method are not satisfied, alternative statistical methods will be employed.

Additional exploratory analyses may be performed to evaluate the robustness and sensitivity of the study results, including but not limited to, additional evaluation of endpoints on other

analysis populations, subgroup analyses, treatment interactions, adjusted or stratified analyses, and/or alternative statistical methods.

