7.1.5 Missing Data Handling

In general, no imputation of missing data is planned for the primary analyses. However, for purposes of any sensitivity analyses, missing data may be imputed using last-observation-carried forward, or other advanced statistical imputation methods.

For the efficacy analyses based on oxygenation parameters, up to Day 6, if the assessment on Day 6 is not available, then the last prior non-missing value, after baseline will be used. See Sections 7.1.2, 7.1.3, and 7.1.4 for algorithm on determining assessments to be used for analysis.

Imputation for P(A-a)O₂ gradient, intubation rate and ordinal scale will not be performed.

If using last observation carried forward, a missing follow-up visit value will be imputed as that patient's previously observed value.

In the absence of any other specifications, the following rule will be used for missing time-toevent data:

• Patients who are alive (not lost to follow up) and did not experience the event of interest will be censored at the date last known to be alive and to be event-free.

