7.4 Analysis Population

The following analysis populations will be used to summarize the results from this study.

- Safety Population includes all patients who received at least one dose of sargramostim and/or SOC based on actual treatment received. Patients who did not receive any study treatment (either sargramostim and/or SOC) will be excluded from Safety Population. All safety analyses will be based on the Safety Population.
- Intent-to-treat Population (ITT) includes all patients who were randomized, and analyzed per the treatment arm as randomized. Selected efficacy analysis (P(A-a)O₂ and intubation rate) may also be performed based on ITT population for the purpose of sensitivity, unless otherwise specified.
- Modified Intent-to-treat Population (MITT): a subset of the ITT population that received at least one dose of any study treatment (either sargramostim and/or SOC). Efficacy analyses will be based on the MITT Population.
- **Per Protocol Population (PP)** includes all patients who were randomized and received at least one dose of sargramostim and/or standard of care based on the treatment assigned

at randomization and meet the eligibility criteria of this study. Selected efficacy analyses may also be performed based on the Per Protocol Population, unless otherwise specified.

- If the ITT, and PP populations are identical, or less than 10% different compared to the MITT population, then the selected efficacy analyses may not be repeated across the ITT and PP analysis population.
- Enrolled Population includes all patients who were eligible and signed informed consent form (ICF).

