7.11.2.2 Mortality

Survival status will be collected up to Day 90 +/- 30 days. Death is considered as an event. All the mortality events and cause of death will be listed by treatment arm and by patient.

Patients who did not experience death within the first 90 days will be censored on the date of Day 90 visit or the date of last contact from the study which ever is earlier.

The number of patients who died and survival time will be summarized by treatment arm. Survival time will also be listed by patient. The probability function of death will be estimated by Kaplan-Meier method. The median time and its 95% confidence interval for each group will be reported. Cumulative progression rates estimated by the KM method for up to day 6, 14, 28, 90 and the 95% confidence intervals will be reported.

The hazard ratio will be estimated by the Cox proportional hazards model with treatment arm as a covariate in the model. Relevant hazard rates, hazard ratio between treatment arms and associated p-values will be tabulated.

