7.12 Safety Evaluations

Safety assessments will include monitoring of available assessments of vital signs, adverse events (AEs), clinical laboratory tests, and physical examinations. The main analysis period would be the Treatment Emergent period which is defined as the period from the date of the first dose until the end of earliest of the following 1) date of Study Day 58 for AEs and date of Study Day 90 for the rest; or 2) date of early discontinuation from study; or 3) data cutoff date. This analysis period will be used for all treatment emergent adverse event, laboratory evaluations. However, serious adverse events analysis will include all the serious adverse events collected after the first dose.

Safety variables will be tabulated and presented for all patients in the Safety Population.

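### The efficacy window in SAP 7.1.3 closes at early study discontinuation while the patient stays in the denominator, so early withdrawals are in effect scored as not intubated, and 7.1.3 conflicts with 7.11.1.2 on later recorded intubations.

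*SAP*

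**What the plan says.** Five parts of the SAP together decide how a patient who leaves the study early enters the Day 14 intubation rate.

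- **Window (7.1.3).** "Analysis period for efficacy parameters would be the period from the date of the first dose until the earliest of the following": Study Day 90, early discontinuation from study, or data cutoff. The adverse-event window in the same section has matching later limbs ("2) date of early discontinuation from study, or 3) data cutoff date") but is followed by an exception for serious events. Section 7.12 repeats it: "serious adverse events analysis will include all the serious adverse events collected after the first dose". Efficacy has no such exception.
- **Denominator (7.1, 7.4).** "Categorical endpoints will be calculated as the percentage of patients with the event, relative to the number of patients in a given analysis population". The efficacy population is MITT, which requires randomization and one dose of any study treatment. It sets no follow-up requirement.
- **Missing data (7.1.5).** "Imputation for P(A-a)O₂ gradient, intubation rate and ordinal scale will not be performed".
- **Primary endpoints (7.11.1, 7.11.1.2).** The opening of 7.11.1 names the Day 14 intubation rate, qualifies it by data availability, and refers to 7.1.2, 7.1.3 and 7.1.4 for choosing the assessments to analyse. Section 7.11.1.2 then counts any intubation from Day 1 to Day 14, with no stop at study discontinuation, and compares the arms by Fisher's exact or chi-square test.
- **Mortality (7.11.2.2).** "Survival status will be collected up to Day 90 +/- 30 days". Death is an event, and only patients who did not die within 90 days are censored, at the Day 90 visit or last contact.

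**The concern.** A binary endpoint with a fixed horizon needs a stated rule for patients not observed to that horizon. Here the rule arises only as a by-product. The window closes at discontinuation, the patient stays in the denominator, and nothing is imputed, so the numerator receives a zero. That amounts to a best-outcome imputation in a plan that says it does not impute this endpoint.

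The second problem is a conflict. If an intubation on Day 5 is in the database for a patient who left the study on Day 3, 7.1.3 excludes it and 7.11.1.2 includes it. Two programmers could follow the SAP faithfully and report different primary results.

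The trial is open label, so withdrawal may depend on both arm and prognosis. Unequal withdrawal then distorts the comparison as well as the level of each rate.

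**Working it through.** **Inputs from the SAP.** 80 sargramostim + SOC and 40 SOC alone (6.1, 7.2). The SAP has no power calculation to reproduce, since 7.2 says the size rests on no statistical assumptions. It gives no intubation or withdrawal rate, so every rate below is an assumption.

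**Step 1: one patient.** A withdrawn patient who would have been an event, or was one after leaving, changes the arm's rate by 1/80 = 1.25 points (sargramostim) or 1/40 = 2.5 points (control).

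**Step 2: level of one arm.** With true control rate r, w withdrawals and Day 14 risk q among them, the expected reported rate is (40r − wq)/40. Take w = 4 and q from r to 2r:

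| True rate r | q = r | q = 2r |
|---|---|---|
| 10% | (4 − 0.4)/40 = 9% | (4 − 0.8)/40 = 8% |
| 20% | (8 − 0.8)/40 = 18% | (8 − 1.6)/40 = 16% |
| 30% | (12 − 1.2)/40 = 27% | (12 − 2.4)/40 = 24% |

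**Step 3: difference between arms.** Reported rate = true rate − (share withdrawn) × (share of the withdrawn who are intubated later, by Day 14). Both true rates are set at 25%.

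- Equal withdrawal in both arms at equal risk: both rates fall, and the difference stays 0.
- Withdrawal 15% sargramostim, 5% SOC: if 25%, 50% or 100% of the withdrawn are later intubated, the spurious difference (sargramostim minus SOC) is −2.5, −5.0 or −10.0 points. At 50%, for example, it is (25 − 7.5) − (25 − 2.5) = 17.5 − 22.5 = −5.0.
- Withdrawal 5% sargramostim, 15% SOC: +2.5, +5.0 or +10.0 points, against sargramostim.

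The probability of p ≤ 0.05 when the true rates are equal, by exact binomial enumeration:

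| Withdrawal (sargramostim / SOC) | Share later intubated | Fisher | Chi-square |
|---|---|---|---|
| none | – | 0.040 | 0.051 |
| 15% / 5% | 50% | 0.086 | 0.107 |
| 15% / 5% | 100% | 0.288 | 0.334 |
| 5% / 15% | 50% | 0.072 | 0.087 |
| 5% / 15% | 100% | 0.231 | 0.262 |

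The 100% rows are extremes.

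**Step 4: a real difference.** With true rates of 20% and 35%, and withdrawal rising from 0% to 15% in both arms at average risk, the difference shrinks from −15.0 to 17.0 − 29.75 = −12.75 points. Chi-square power falls from 0.44 to 0.37.

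**Step 5: effect of the missing rule on a reported result.** Assume 16/80 and 12/40 observed intubations, and withdrawals without an observed intubation as shown.

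| Handling of withdrawals | 8 and 4 withdrawn | 12 and 2 withdrawn |
|---|---|---|
| non-events | 20.0% vs 30.0%, p = 0.26 | 20.0% vs 30.0%, p = 0.26 |
| excluded | 16/72 = 22.2% vs 12/36 = 33.3%, p = 0.25 | 16/68 = 23.5% vs 12/38 = 31.6%, p = 0.37 |
| events | 24/80 = 30.0% vs 16/40 = 40.0%, p = 0.31 | 28/80 = 35.0% vs 14/40 = 35.0%, p = 1.00 |
| bounds on difference | −20 to 0 points | −15 to +5 points |

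The p-values are Fisher's exact. With unequal withdrawal, the apparent 10-point advantage depends on how the withdrawals are handled.

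**The case against.** The strongest reply is that the endpoint sections are the specific rules and 7.1.3 only the general one.

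- **Intubation.** 7.11.1.2 counts any intubation in Days 1–14, so one recorded after discontinuation would naturally be included. A reader might infer from 7.1.3 alone that such events are definitely discarded. The SAP does not settle that. Equally, it does not settle the reverse, because 7.11.1 sends the reader to 7.1.3 for the primary endpoints. The conflict stands.
- **Denominator.** No section says outright that withdrawals are non-events, and the data-availability qualifier in 7.11.1 permits an observed-data denominator. That is fair. But the qualifier defines no denominator, whereas 7.1 does, so at best it adds a second reading.
- **Deaths.** A reader might infer that a death after study discontinuation is kept as a serious event but lost from the mortality analysis. The documents do not support this. Under 7.11.2.2 a known death within 90 days is an event, and it would be lost only if 7.1.3 overrode that section, which the SAP nowhere says. No mortality bias is shown.
- **Existing safeguards.** 7.5 reports completion of Day 14 and study withdrawals by arm. The sensitivity analyses in 7.11.1.3 change only the population, and 7.4 lets them be skipped when populations differ by less than 10%. Other imputation in 7.1.5 is optional and unspecified. None of these bounds the effect.
- **Size.** All analyses are declared descriptive, and withdrawal may prove rare. It is tempting to show a p-value shift, such as Fisher 0.055 for 8/80 against 10/40 becoming 0.157 against 8/40. With four control withdrawals that requires half of them to be events and no loss in the other arm, so it should not carry the argument. Descriptive status does not remove bias from an estimate.

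The protocol's discontinuation criteria are not available here, so how often intubation data exist after a patient leaves the study is unknown.

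**Conclusion.** The point holds in this form. Read together, 7.1, 7.1.3, 7.1.5, 7.4 and 7.11.1 in effect score a patient who leaves the study before Day 14 without an intubation as not intubated. For intubations recorded after discontinuation, 7.1.3 and 7.11.1.2 conflict and no precedence is given. For mortality, only a statement of precedence is missing.

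The bias can run in either direction and is bounded by 2.5 points per withdrawn control patient and 1.25 per withdrawn sargramostim patient. Under the assumed 25% true rates and 15% versus 5% withdrawal, it is 2.5 to 10 points in the difference. It vanishes from the difference, though not from the levels, if the true rates, withdrawal and risk after withdrawal are equal across arms. It concerns only patients leaving the study, not those stopping treatment alone. This should be corrected before database lock because it affects one of the two primary measures and is cheap to fix.

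**What to change.** 1. In 7.1.3, state that the event windows in 7.11.1.2 and 7.11.2.2 prevail over the general efficacy period. Count every recorded intubation to Day 14 and every recorded death to Day 28 and Day 90, whether before or after study discontinuation.
2. In 7.11.1.2, report by arm the number of patients whose Day 14 intubation status is unknown.
3. Estimate the Day 14 intubation rate by cumulative incidence, with death before intubation as a competing event and censoring at the last date on which intubation status is known.
4. That censoring assumes withdrawal is uninformative, which is doubtful in an open-label trial. Add a best/worst-case sensitivity analysis counting the unknowns as non-events and as events, both the same way in each arm and in opposite directions between arms. Amend 7.1.5 so that its no-imputation statement does not bar this analysis.

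The cost is a few sentences, one extra table and a slightly wider interval for the Day 14 rate. No new data collection is implied, because the change uses what is already recorded.

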7.1.4 Post-Treatment: Up to Day 6 (or Discharge, whichever is earlier)

The post-treatment evaluation is one of the main timepoints for evaluation of efficacy endpoints, particularly measures of oxygenation. In the protocol, this is referred to as the Day 6 evaluation. In the context of this document, this will be presented as "Up to Day 6".

For the **sargramostim arm**: any assessment that is performed within 24 hours after the last treatment administration date/time may be considered as the "Up to Day 6" evaluation. That is, within last dose date/time + 24 hours. If there are no assessments in that timeframe, then the last

post-baseline observation prior to last dose date/time will be used. To address any missing dose times for the known dose dates:

- if the start time of inhalation dosing is known, then the end time can be assumed to be 15 minutes later (i.e., end time = start time + 15 minutes)
- otherwise, the end time will be assumed to be 23:59

For patients who received **standard of care alone**, any assessment that is within 1 calendar day after the later of, the treatment completion (or treatment discontinuation date) [from the treatment disposition CRF page] or Day 6/Post-Treatment visit date, may be considered as the "Up to Day 6" evaluation. If there are no assessments in that timeframe, then the last postbaseline observation prior to latter of, the treatment completion (or treatment discontinuation date) or Day 6/Post-Treatment visit date, will be used.

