7.1.1 Study Day

Study day will be calculated as follows:

- For the sargramostim arm: Assessments/events prior to the first sargramostim dose date, study day will be the assessment date minus the first dose date. The end of treatment is the date/time of the last administered dose of sargramostim.
- For the control arm, the randomization date will be used as the first dose date. The treatment completion or discontinuation date/time from the treatment disposition CRF page will be considered the end of treatment for the SOC arm.
- Assessments/events on or after the first dose date, study day will be the assessment date minus the first dose date plus one.
- The duration of SOC (for both treatment arms) will be based on the start date of randomization, and the end date as latest of 1) any concomitant medication end date with indication "COVID-19", or 2) any end date of procedure with indication "COVID-19", or 3) any end date of transfusion, ventilation or supplemental oxygen.

For assessments captured as an unscheduled visit, if the date of assessment is the same as a date of another visit (e.g., Day 6, Day 14, Day 28, Day 58, Day 90), then the visit label for the unscheduled assessment can be re-assigned to the appropriate visit label (e.g., Day 6, Day 14, Day 28, Day 28, Day 58, Day 90). Other appropriate data handling approaches may be used to ensure data is analyzed in the appropriate timepoint analysis.

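### Section 7.1.4 selects the 'Up to Day 6' oxygenation value by different rules in the two arms: sargramostim values can be lost or read early, control values can be read late

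*SAP*

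**What the plan says.** Section 7.1.4 has one paragraph per arm.

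- **Sargramostim.** "any assessment that is performed within 24 hours after the last treatment administration date/time may be considered as the" reading for this timepoint. If there is none, the last "post-baseline observation prior to last dose date/time will be used". If a dose has a start time but no end time, 15 minutes are added; "otherwise, the end time will be assumed to be 23:59".
- **SOC alone.** The candidate is "any assessment that is within 1 calendar day after the later of, the treatment completion (or treatment discontinuation date" on the disposition page) and the Day 6/Post-Treatment visit date. If there is none, the rule takes the most recent value after baseline: "observation prior to latter of, the treatment completion (or treatment discontinuation date) or Day 6/Post-Treatment visit date, will be used".

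Section 7.1.5 covers both arms together. It turns to the last earlier post-baseline oxygenation value only when the Day 6 assessment is missing, and refers to 7.1.4 for the algorithm. It also says that P(A-a)O2 is not imputed.

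Section 7.11.1 states that ABG was required only at baseline and at the Day 6/Post-Treatment visit, or at discharge if earlier. Section 7.11.1.1 sends the P(A-a)O2 percent-change categories and the ≥33% responder comparison to the 7.1.4 algorithm. Section 7.1 expresses categorical endpoints "relative to the number of patients in a given analysis population".

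**The concern.** P(A-a)O2 by Day 6 is one of the two primary endpoints, and a randomised comparison needs it read at comparable times in both arms. Here the reading depends on events after randomisation, and differently by arm. With sargramostim, it depends on when dosing stopped and at what hour. With SOC alone, it depends on whether the recorded completion date falls after Day 6.

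Few ABGs were mandatory, so a sargramostim patient whose Day 6 ABG is ruled out often has no post-baseline value at all, or only an optional early one. A control can be read after Day 6, although the heading of 7.1.4 limits the timepoint to Day 6 or discharge. What is at stake is a difference in missingness and timing between arms, which would distort a descriptive estimate.

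**Working it through.** **Step 1. Apply both rules to the same times.** For sargramostim, an ABG is in the window if last dose ≤ ABG ≤ last dose + 24 h, is a fallback if before the last dose, and otherwise is neither. For SOC alone, let A be the later of the completion and visit dates. An ABG is in the window if its date is A or A + 1 and is a fallback if before A. I count date A itself as in the window and place the visit on Day 6. The SOC column uses the same day as the completion date.

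| Last dose (or SOC completion) | ABG | Gap from dose | Sargramostim | SOC alone |
|---|---|---|---|---|
| Day 5 09:00 | Day 6 08:00 | 23 h | window | window |
| Day 5 08:15 | Day 6 10:00 | 25 h 45 min | neither | window |
| Day 5, time unknown, set to 23:59 | Day 6 10:00 | 10 h 1 min | window | window |
| Day 4 09:00 | Day 6 10:00 | 49 h | neither | window |
| Day 3 09:00 | Day 6 10:00 | 73 h | neither | window |
| SOC completion Day 10 | Day 6 | – | – | fallback only |
| SOC completion Day 10 | Day 11 | – | – | window |

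Rows 2 and 3 are the same ABG, rejected when the dose time is recorded and accepted when it is not. The last two rows show the drift on the control side.

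**Step 2. Compare with 7.1.5.** In rows 2, 4 and 5 a Day 6 assessment exists. Section 7.1.5 would have no reason to look elsewhere, whereas 7.1.4 does not admit it.

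**Step 3. Illustrate the size.** The SAP gives no stopping rate, clock times or responder rate, so every input below is assumed except the planned 80 and 40 patients.

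*Completers whose Day 6 ABG is excluded.* Let x be the excluded share of the sargramostim arm, with a responder rate of 40%.
- MITT denominator: fall = 0.40x. For x = 5/10/20% (4, 8 or 16 of 80 patients) this is 2/4/8 points.
- Only patients with a value: shift = x(0.40 − r)/(1 − x), where r is the rate among those excluded. It is 0 if r = 40%, +1.1/+2.2/+5.0 points if r = 20%, and the same amounts downward if r = 60%.
- Plausible x: with ABG times uniform over 06:00–12:00 on Day 6, x is 83% if the Day 5 dose ended uniformly over 06:00–08:00, 50% for 08:00–10:00, and 0% for noon or later.

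*Early stoppers.* Assume a mean improvement of 5 percentage points per day with SD 30, so the responder rate is Φ((−33 + 5 × days)/30). On Day 6 (5 days) r6 = Φ(−0.267) = 39.5%; on Day 3 (2 days) r3 = Φ(−0.767) = 22.2%. Let s = 10% stop early, and let a share q of them have an optional early ABG.
- MITT denominator: fall = s(r6 − q·r3) = 3.9/2.8/1.7 points for q = 0/50/100%.
- Only patients with a value: r6 − [(1 − s)r6 + s·q·r3]/[1 − s(1 − q)] = 0/0.9/1.7 points.

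*Scale.* The SE of the responder difference at 40% is √(0.24/80 + 0.24/40) = √0.009 = 9.5 points.

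The late control readings are not modelled. Their effect depends on how patients still on SOC after Day 6 are changing.

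**The case against.** The wording is permissive: the in-window value only may be considered, and Section 7.1.1 adds "Other appropriate data handling approaches may be used to ensure data is analyzed in the appropriate timepoint analysis". An analyst could read 7.1.5 as overriding the 24-hour limit. That supports calling this a conflict to reconcile. It does not remove it, because neither phrase says which value is used.

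A reader might infer that the excluded ABG is unusable throughout. The SAP does not support that: the value can still enter the by-day MMRM, the maximum change over the study and the listing. Section 7.11.1.1 says the change up to Day 6 is evaluated by that MMRM.

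A reader might also infer that only sargramostim readings depend on when treatment ended. The SOC 'later of' anchor shows otherwise.

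Nor does the SAP support a known bias against sargramostim. On the MITT denominator, lost values lower that arm's rate. But Sections 7.11 and 7.11.1 speak of available data, and on that denominator the direction depends on who is excluded.

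The early-stopper case relies on the Day 6/Post-Treatment visit staying in place after an early stop. If the protocol, which is not shown, moves the visit forward, that case shrinks. The completer case in row 2 does not depend on this.

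Finally, the last-earlier-value step in 7.1.5 can be read as derivation rather than imputation, so its no-imputation sentence needs clarifying but is not a separate error. Against all this, "All analyses will be considered as descriptive analyses" limits what is at stake without making unlike readings comparable.

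**Conclusion.** The point holds as a two-sided difference in how the arms are read. In the sargramostim arm, a Day 6 ABG more than 24 hours after the last dose is in neither the window nor the fallback. In the SOC arm, a Day 6 ABG is always eligible but can be displaced by a later value. Sections 7.1.4 and 7.1.5 disagree for sargramostim.

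The reach is the percent-change categories, the ≥33% responder comparison (and any alternative cutoffs) and probably the waterfall plot. Intubation by Day 14 is unaffected.

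The size cannot be set from the SAP. The sargramostim-side effect is zero if nobody stops early and every Day 6 ABG falls within 24 hours of the last dose; the control-side effect is zero if no control is read past Day 6. All the shifts shown are below the 9.5-point SE and rest on assumed inputs. This should be fixed before database lock, but it does not invalidate the plan.

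**What to change.** In 7.1.4, replace the two arm paragraphs with one rule, applied in both arms whenever treatment stopped:

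- **Anchor:** the Day 6/Post-Treatment visit date, or the day of discharge if earlier. If neither is recorded, for example after death or withdrawal before Day 6, use the calendar date of Study Day 6.
- **Value:** the assessment on the anchor date or within 1 calendar day after it, taking the one closest to the anchor. If there is none, use the last post-baseline value before the anchor.
- **Drop** the SOC 'later of' completion anchor from the main analysis.
- **Keep** the value within 24 hours of the last dose as a sensitivity analysis. The 15-minute and 23:59 conventions then serve only that analysis and treatment duration in 7.10.

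In 7.1.5, say that the last-earlier-value step is part of the derivation for P(A-a)O2 and that no other imputation of it is done. Report by arm the number of MITT patients with no value.

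The cost is SAP wording and one changed derivation, with no new data. Some main readings will lie more than 24 hours after the last dose, which the sensitivity analysis covers. A patient whose only post-baseline ABG came more than a day after the anchor would have no value in the main analysis.
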